21.3.5 Adherence and Retention Analyses

Adherence to the protocol will be assessed with a smartphone-assisted medication adherence platform [119] in which the subject takes a video of drug administration at each dose, and transmits this to study personnel. This program has been used successfully in previous studies, and includes security provisions that ensure protection of confidentiality and privacy. Circulating concentrations of CBD will also be collected at T1-T8 to verify treatment adherence.

Number of participants that complete the treatment phase of the study (through T8), complete the follow-up phase of the study (through T9), and are lost to follow-up will be collected. Frequency of and reasons for discontinuation of the intervention or study follow-up will also be tallied.

21.3.6 Baseline Descriptive Statistics

Treatment groups will be compared on several baseline characteristics, including sex, age, race/ethnicity, education level, baseline measures of alcohol consumption (% drinking days and % heavy drinking days), alcohol craving (PACS), anxiety (BAI), mood (BDI-II), and self-efficacy (AASE). Categorical data will be tallied, and means and standard deviations of continuous scores will be calculated.

21.3.7 Planned Interim Analysis

21.3.7.1 Safety Review

The DSMB will meet (in person or by teleconference) following completion of treatment of the first 5 completers, after completion of treatment of the first 20 completers, and upon completion of enrollment for the trial. Prior to

CONFIDENTIAL

This material is the property of the NYU School of Medicine and Langone Health
Do not disclose or use except as authorized in writing by the study sponsor

each meeting, the PI will prepare a report to the Board including review of the aggregate analysis of adverse events/serious adverse events.

Following each meeting, the board will provide the PI with a report including a recommendation to continue the study unchanged, continue with modifications of the protocol and/or the consent form to protect participant safety, or terminate the study. The study may be stopped if there are untoward and concerning levels of AE or SAE outcomes attributable to CBD or study participation. If the DSMB finds it is likely that CBD is contributing to negative outcomes, they will consider solutions including protocol changes or potentially stopping the study.

21.3.8 Multiple Comparison/Multiplicity

Because our primary outcomes are safety data, in which we hypothesize a null difference between treatment groups, we will not employ a correction for Type I error/alpha inflation.

21.3.9 Tabulation of Individual Response Data

Aside from AEs/SAEs, individual response data will not be presented.

21.3.10 Exploratory Analyses

Hypothesis E will be assessed by comparing within- and between- group differences in percent heavy drinking days from baseline (T1) to week 8 of treatment with study medication (T7) and during the 4-week period following administration of study medication (T8-T9)

21.4 Sample Size

We will enroll approximately 60 participants, and randomize approximately 40 participants to meet our recruitment goal (through week 8/T7). Sensitivity to detect effects with the proposed study design was calculated for each hypothesis at power = 0.95 for univariate outcomes with 40 participants in 2 groups at alpha = 0.05 for the analyses described above. Hypotheses 1a and 1c are powered to detect effect sizes of approximately $d = 0.2$. Hypotheses 2a and 2b are powered to detect effect sizes of $d = 0.2$ and $d = 0.3$, respectively. Hypothesis E (exploratory hypothesis) is powered to detect an effect size of $d = 0.6$, therefore we are only powered to detect substantial impacts on drinking outcomes for this exploratory aim.

22 Source Documents and Access to Source Data/Documents

Source data is all information, original records of clinical findings, observations, or other activities in a clinical trial necessary for the reconstruction and evaluation of the trial. Source data are contained in source documents. Examples of these original documents, and data records include: hospital records, clinical and office charts, laboratory notes, memoranda, subjects' diaries or evaluation checklists, study medication dispensing records, recorded data from automated instruments, copies or transcriptions certified after verification as being accurate and complete, microfiches, photographic negatives, microfilm or magnetic media, x-rays, subject files, and records kept at the dispensation site, at the laboratories, and at medico-technical departments involved in the clinical trial. It is acceptable to use CRFs as source documents. If this is the case, it should be stated in this section what data will be collected on CRFs and what data will be collected from other sources.

The study case report form (CRF) is the primary data collection instrument for the study. All data requested on the CRF must be recorded. All missing data must be explained. If a space on the CRF is left blank because the procedure was not done or the question was not asked, write "N/D". If the item is not applicable to the individual case, write "N/A". All entries should be printed legibly in black ink. If any entry error has been made, to correct such an error, draw a single straight line through the incorrect entry and enter the correct data above it. All such changes must be initialed and dated. DO NOT ERASE OR WHITE OUT ERRORS. For clarification of illegible or uncertain entries, print the clarification above the item, then initial and date it.

Access to study records will be limited to IRB-approved members of the study team. The investigator will permit study-related monitoring, audits, and inspections by the IRB/EC, the sponsor, government regulatory bodies, and University compliance and quality assurance groups of all study related documents (e.g. source documents, regulatory documents, data collection instruments, study data etc.). The investigator will ensure

CONFIDENTIAL

This material is the property of the NYU School of Medicine and Langone Health
Do not disclose or use except as authorized in writing by the study sponsor

the capability for inspections of applicable study-related facilities (e.g. dispensation site, diagnostic laboratory, etc.).

Participation as an investigator in this study implies acceptance of potential inspection by government regulatory authorities and applicable University compliance and quality assurance offices.

23 Quality Assurance and Quality Control

Data quality assurance (QA) includes all those planned and systematic actions that are established to ensure that the trial is performed and the data are generated, documented (recorded), and reported in compliance with GCP and the applicable regulatory requirements(s) (ICH E6 1.46). Data quality control (QC) includes the operational techniques and activities undertaken within the quality assurance system to verify that the requirements for quality of the trial-related activities have been fulfilled (ICH E6 1.47).

QC procedures will be implemented beginning with the data entry system, and data QC checks on the database will be generated. Any missing data or data anomalies will be communicated to the site(s) for clarification/resolution.

Following written SOPs, the monitors will verify that the clinical trial is conducted and data are generated, documented (recorded), and reported in compliance with the protocol, GCP, and the applicable regulatory requirements (e.g., Good Laboratory Practices (GLP), Good Manufacturing Practices (GMP)). The investigational site will provide direct access to all trial related sites, source data/documents, and reports for the purpose of monitoring and auditing by the sponsor, and inspection by local and regulatory authorities.

24 Ethics/Protection of Human Subjects

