21.2 Statistical Hypotheses

Hypothesis 1a: Within-group circulating CBD levels will stabilize within one week, i.e. pre-CBD dosing (12 hour) levels obtained after 1 week of treatment will not differ from those obtained after 4 weeks of treatment at each dose.

Hypothesis 1b: Circulating CBD levels obtained at the 1200 mg/day dose will be comparable to those associated with anti-additive effects in animal models, i.e., in the range of 200-400 ng/ml.

Hypothesis 1c: No clinically significant cognitive or motoric impairments, CBD-related serious adverse events, or persisting adverse effects will be observed.

Hypothesis 2a: Relative to placebo, CBD will improve self-report measures of craving, anxiety, mood, and self-efficacy.

Hypothesis 2b: Relative to placebo, CBD will be associated with decreased stress- and alcohol cue-induced craving and physiological stress response

Hypothesis E: Relative to the placebo-treated group, CBD-treated participants will have fewer heavy drinking days during and for four weeks after treatment with 1200mg/day CBD vs. placebo.

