21.3.2 Analysis of the Primary Endpoint(s)

For Hypothesis 1a, acute circulating levels of CBD will be assessed in CBD-treated participants 45 minutes after initial administration (T1, T4), and 45 minutes after administration of the morning dose of medication following 1 day (T2, T5), 1 week (T3, T6), and 4 weeks (T4, T7) of treatment with each dose of CBD. Additionally, circulating levels of CBD will be assessed in CBD-treated participants 12 hours after ingestion of the preceding evening dose following 1 week (T3, T6) and 4 weeks (T4, T7) of administration of each dose of CBD. Levels of CBD (mean and standard deviation) will be reported at each timepoint and effects of dose and timepoint will be evaluated. For Hypothesis 1b, circulating CBD levels (mean and standard deviation) 45 minutes after administration of the morning dose of medication following 1 week (T3, T6) and 4 weeks (T4, T7) of treatment with each dose of CBD will be reported in CBD-treated participants. For Hypothesis 1c, between-group differences on psychomotor tasks (T1-T8), cognitive measures (T3, T6) and number of adverse events (T1-T9) will be assessed.

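### The stated 95% power at d = 0.2 is not delivered for Hypothesis 1a, the cognitive part of 1c, or 2a read as a baseline-adjusted group difference

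*Combined protocol and SAP*

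**What the plan says.** Section 21.4 sets the conditions of the sensitivity calculation: "at power = 0.95 for univariate outcomes with 40 participants in 2 groups at alpha = 0.05 for the analyses described above". It then lists the effects said to be detectable:

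- Primary hypotheses: "Hypotheses 1a and 1c are powered to detect effect sizes of approximately $d = 0.2".
- Secondary hypotheses: "Hypotheses 2a and 2b are powered to detect effect sizes of $d = 0.2$ and $d = 0.3$, respectively".
- Exploratory: "Hypothesis E (exploratory hypothesis) is powered to detect an effect size of $d = 0.6", with a remark that only substantial effects on drinking could be found.

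It does not give sidedness, a within-person correlation, the number of measurements, the contrast being powered, or an allowance for dropout.

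The analyses it refers back to are these:

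- **1a.** Section 21.2 predicts that pre-dose "levels obtained after 1 week of treatment will not differ from those obtained after 4 weeks of treatment at each dose". Section 21.3.2 restricts the data to one arm: "circulating levels of CBD will be assessed in CBD-treated participants 12 hours after ingestion of the preceding evening dose". It adds that "effects of dose and timepoint will be evaluated".
- **1c.** Section 21.3.2 compares groups on cognitive measures at T3 and T6 only. Section 8.3.2 lists no cognitive testing at T1, and Section 21.3.1 names no cognitive covariate.
- **2a.** The prediction is relative to placebo. Section 21.3.3 uses T1 and five later visits, and Section 21.3.1 adds baseline scores as covariates.
- **2b.** The prediction is that "CBD will be associated with decreased stress- and alcohol cue-induced craving and physiological stress response". Section 21.3.3 models three periods and three scripts at both T3 and T6. Sections 5.1.2 and 8.1 schedule the task at week 5 only.
- **E.** Section 21.3.10 compares percent heavy drinking days within and between groups, from baseline to week 8 and over the four weeks after treatment.

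Section 7.1.9 limits the primary analyses to participants who complete eight weeks, and Section 6.6.2 says dropouts are not replaced.

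**The concern.** An effect of d = 0.2 is small. A plain comparison of two groups of 20 has almost no chance of finding it, so 95% power would need a very large gain from repeated measurement. Three of the five stated figures are 0.2, although the designs behind them differ greatly: one arm measured in pairs, two groups measured twice without a baseline, and two groups measured six times.

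The figure matters because the primary predictions are null. Section 21.3.8 says no group difference is expected on the safety outcomes, and 1a predicts no change between week 1 and week 4. A non-significant result is therefore the predicted result, and Section 21.4 is where a reader learns how small an effect would have shown up. As written, it implies that a cognitive effect, or CBD accumulation, of d = 0.2 would be missed only 5% of the time.

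**Working it through.** **Inputs.** From the plan: power 0.95, alpha 0.05, 40 randomised 1:1 (20 per arm), and the visits listed above. Assumed: two-sided tests, no dropout, and an equal correlation ρ between repeated measures, shown as a range. Power is exact, from the noncentral t or F distribution.

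**Reference, two groups of 20.** Noncentrality is d / √(2/20) on 38 df. The d detectable at 95% power is 1.170. Power at d = 0.2 is 9%, and 95% would need about 650 per arm. The stated 0.2 does not reproduce here.

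**1a, CBD arm, 20 pairs.** The detectable standardised change is dz = 0.850. In between-person SD units, d = dz·√(2(1−ρ)) at one dose, or dz·√(1−ρ) if the change is averaged over both doses.

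| ρ | d per dose | power at 0.2 | d pooled | power at 0.2 |
|---|---|---|---|---|
| 0.5 | 0.85 | 14% | 0.60 | 22% |
| 0.8 | 0.54 | 27% | 0.38 | 48% |
| 0.9 | 0.38 | 48% | 0.27 | 77% |

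To reach 0.2, ρ must be 1 − (0.2/0.850)²/2 = 0.97 per dose, or 1 − (0.2/0.850)² = 0.945 pooled.

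**1c cognitive, mean of T3 and T6.** Detectable d = 1.170·√((1+ρ)/2).

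- ρ = 0: 0.83, power at 0.2 is 14%.
- ρ = 0.5: 1.01, power 11%.
- ρ = 0.9: 1.14, power 10%.

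Higher correlation makes this worse, so no correlation in the range rescues the figure. One-sided, the detectable d is still 0.75 at ρ = 0 and 0.92 at 0.5.

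**2a, mean of five later visits adjusted for baseline.** Detectable d = 1.170·√((1+4ρ)/5 − ρ²).

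- ρ = 0.5: 1.170·√0.35 = 0.69, power at 0.2 is 18%.
- ρ = 0.7: 1.170·√0.27 = 0.61, power 22%.
- ρ = 0.9: 1.170·√0.11 = 0.39, power 46%.

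Reaching 0.2 needs ρ of about 0.975.

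**Omnibus group-by-time F test, the most favourable reading.** λ = f²·40·m/(1−ρ), with m − 1 and 38(m − 1) df, and d = 2f for two groups.

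- 2a, m = 6, d = 0.2 (f = 0.1): 34% at ρ = 0.5; 95% at ρ of about 0.88.
- 2a, m = 6, with 0.2 read as f: λ = 0.04·240/0.5 = 19.2, power 94% at ρ = 0.5.
- 1c cognitive, m = 2, with 0.2 read as f: λ = 0.04·80/0.5 = 6.4, power 69% at ρ = 0.5.
- 2b, m = 18, d = 0.3: λ = 0.0225·720/0.5 = 32.4, power 97% at ρ = 0.5. With the 9 cells of a single visit, 82%.
- E, m = 2, d = 0.6: λ = 0.09·80/0.5 = 14.4, power 96% at ρ = 0.5.

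**Other contrasts for 2b and E (illustrative only).**

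- 2b, imagery minus pre-imagery, stress and cue averaged against neutral, two visits: detectable d = 1.170·√(1.5(1−ρ)). Power at 0.3 is 19%, 28% and 39% at ρ = 0.5, 0.7 and 0.8.
- E, one baseline-adjusted value: detectable d = 1.170·√(1−ρ²). Power at 0.6 is 57% at ρ = 0.5, and 95% needs about 0.86.

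**Confidence intervals.** The 95% half-width for a single 20 versus 20 comparison is t(38)·√(2/20) = 0.64 SD. With 16 completers per arm (an assumption) it is 0.72 SD, and the detectable d rises from 1.17 to 1.32.

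**The case against.** The best defence is that Section 21.4 powered omnibus repeated-measures tests. Section 21.3.1 does specify mixed models with time as a within-subject factor, and Section 21.3.3 asks for between- and within-group differences at six visits. This defence stands in part. On such a test 2a reaches d = 0.2 at a correlation near 0.88, and the figures for 2b and E reproduce at 0.5.

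A reader might therefore infer from the shortfall that every figure in Section 21.4 is wrong, or that 2a cannot reach 0.2 on any test. The documents support neither inference, because no contrast or correlation is named. It would equally be too strong to say that E requires a correlation of 0.80 or more: that holds for a baseline-adjusted comparison, not for the two-measure interaction.

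The defence does not help 1a, which has one arm, or cognitive 1c, where a T3-to-T6 interaction is not the safety question and would itself need a correlation of about 0.985.

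It can also be said that this is a proof-of-concept study, that the figures are described as sensitivity rather than as the basis of the sample size, and that Section 21.1 defers a formal SAP. Those points limit the consequences but do not make the printed figures right.

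**Conclusion.** The claim of 95% power at d = 0.2 is wrong as written for 1a and for cognitive 1c, and for 2a when the question is a baseline-adjusted difference from placebo. In place of a 5% chance of missing such an effect, the recomputed chance is 86–90% for cognition (ρ from 0 to 0.9) and 52–86% per dose for accumulation (ρ from 0.5 to 0.9). For 2a, 0.2 at a correlation of 0.5 fits only if it is Cohen's f, which corresponds to d = 0.4. A mix-up of d and f is therefore possible, though not established.

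The 0.3 for 2b and 0.6 for E are unsupported, not shown to be wrong. The 18 cells behind 0.3 also depend on a T3 session that Sections 5.1.2 and 8.1 do not schedule. The psychomotor and adverse-event parts of 1c were not assessed here.

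These results rest on equal correlations, two-sided tests and 20 evaluable per arm. The last is a best case under Sections 7.1.9 and 6.6.2. One-sided testing does not change the conclusion: 1a per dose would still need a correlation of about 0.966. A reader might also infer that the trial should be larger. That does not follow, because the defect lies in the stated sensitivity.

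**What to change.** Keep 40 participants and revise Section 21.4, carrying the changes into the SAP:

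- Replace d = 0.2 for 1a, cognitive 1c and 2a with recomputed detectable effects and their assumed correlation ranges. Use n = 20 for 1a and say whether it is tested per dose or pooled.
- For each hypothesis state the test, sidedness, effect metric (d, dz or f), contrast and evaluable number. Label figures at 20 per arm as best case.
- Reconcile Section 21.3.3 with Sections 5.1.2 and 8.1 on when the cue and stress task is done. Then keep 0.3 and 0.6 only alongside the contrast, number of measures and correlation that produce them. Mark any power grid for 2b or E as illustrative.
- Report safety comparisons with 95% confidence intervals, noting the expected half-width of about 0.64 SD for a single comparison, wider with dropout. State that a non-significant safety comparison does not exclude small or moderate effects.

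The cost is rewording one section, settling the task schedule, and accepting a less favourable statement of sensitivity. No participants or visits are added.

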24.1 Ethical Standard

The investigator will ensure that this study is conducted in full conformity with Regulations for the Protection of Human Subjects of Research codified in 45 CFR Part 46, 21 CFR Part 50, 21 CFR Part 56, and/or the ICH E6.

24.2 Institutional Review Board

The protocol, informed consent form(s), recruitment materials, and all participant materials will be submitted to the IRB for review and approval. Approval of both the protocol and the consent form must be obtained before any participant is enrolled. Any amendment to the protocol will require review and approval by the IRB before the changes are implemented to the study. All changes to the consent form will be IRB approved; a determination will be made regarding whether previously consented participants need to be re-consented.

24.3 Informed Consent Process

24.3.1 Consent/Accent and Other Informational Documents Provided to Participants

Consent forms describing in detail the study agent, study procedures, and risks are given to the participant and written documentation of informed consent is required prior to starting intervention/administering study product.

The following consent materials are submitted with this protocol:

- Advertisement
- Telephone Screening Consent Form
- Telephone Screening Script
- Informed Consent Form
- Consent Quiz
- Audio-Visual Release Form

CONFIDENTIAL

This material is the property of the NYU School of Medicine and Langone Health
Do not disclose or use except as authorized in writing by the study sponsor

24.3.2 Consent Procedures and Documentation

An IRB-approved pre-screening form will be used to pre-screen individuals expressing interest in the study, to assess whether they are likely to qualify for the study. Interested patients who pass the pre-screening will be referred for informed consent.

Interested patients will be provided with an informed consent form including all pertinent details of the study including description of the following: the assessment interview and questionnaires; the follow-up interviews; description of experimental treatment; risks and benefits of study procedures; alternatives to participation in the study; confidentiality; emergency treatment and compensation for injury; payment for participation; a statement that patients will be informed of any new findings affecting the risks or benefits of the study; a statement that participation is voluntary and that the patient may withdraw at any time; and information about whom to contact with questions or in case of emergency. The consent form will also include assurances of confidentiality and a statement that participation is entirely voluntary, that the decision to participate will in no way influence other aspects of the patient's treatment, and that the participant is free to withdraw participation at any time. The investigator will explain the research study to the participant and answer any questions that may arise. All participants will receive a verbal explanation in terms suited to their comprehension of the purposes, procedures, and potential risks of the study and of their rights as research participants. Participants will have the opportunity to carefully review the written consent form and ask questions prior to signing.

In the event the participant cannot be at the study site to participate in the consent process in person, it can be conducted via telephone or NYULH-approved Secure Video Conferencing (i.e. WebEx). An electronic copy of the consent form will be shared with the participant via SendSafe email and participants will still be given adequate time to read, review and ask questions about the informed consent document. Participants can electronically sign and date the consent form and authorization documents by typing their names, initials and date and/or using a valid electronic signature wherever indicated. Once signed, participants will return the informed consent form and authorization documents to the consenting study team member via SendSafe email. The consenting study team member will then electronically sign the informed consent form and authorization forms where indicated and return the completed and double-signed consent documents to the participant for their personal record keeping via SendSafe email correspondence. Should the participant prefer, they can print and sign a hard copy of the document to be mailed or scan and email the documents via SendSafe back to the consenting study team member.

The participants may withdraw consent at any time throughout the course of the trial. A copy of the signed informed consent document will be given to the participants for their records. The rights and welfare of the participants will be protected by emphasizing to them that the quality of their medical care will not be adversely affected if they decline to participate in this study.

A copy of the signed informed consent document will be stored in the subject's research record. The consent process, including the name of the individual obtaining consent, will be thoroughly documented in the subject's research record. Any alteration to the standard consent process (e.g. use of a translator, consent from a legally authorized representative, consent document presented orally, etc.) and the justification for such alteration will likewise be documented.

Patients who consent to participate in the study will also be invited to consent to having their remote and/or in-person screening assessments (i.e. SCID) audio-recorded at the initial visit (see Audio Recording Consent). If a patient does not sign the Audio Recording Consent, then we will not audio-record the patient's interview.

